- (2) Enroll a single-arm, open-label trial of **40** Ocrelizumab-treated MS patients who are soon starting GLP-1 agonists, monitored prospectively for 2 years to measure MS **progression** (clinical disability worsening, stability or improvement) every 3 months, including (a) clinical assessments (e.g. EDSS, 25-foot timed walk, SDMT) as used in the ORATORIO trial of Ocrelizumab, (b) PROMs on progression in MS including fatigue, ambulation distance, mood; and (3) simple objective biomarkers of disease (e.g. plasma neurofilament light chain, glial fibrillary acidic protein).

Overview: Aims 1 and 2 will recruit participants simultaneously but draw upon MS participants at different points in their GLP-1 agonist treatment. Participants can enroll in either the cohort of Aim 1 (in-person or remote) or the open label trial of Aim 2 (in-person only), not both aims. All participants will be Ocrelizumab-treated for MS upon study enrollment.

Study Endpoints

The primary outcome measure is **PIRA** (progression independent of relapse activity), based primarily on clinical assessment, dichotomized as present or not.¹²

For Aim 1, the cohort, patient-derived disability status (PDDS) score, and ambulation score (self-reported) will be the primary endpoints of interest.

For Aim 2, the clinical trial, PIRA will be measured pre-GLP-1 start and at study end (week 72). A composite score of disability, similar to the ORATORIO¹³ trial will be constructed including EDSS score, 25-foot timed walk, 9-hole peg test, and SDMT score.

Study Interventions/ Investigational Agent

Glucagon-like peptide-1 agonist agent is the study agent of interest. This study will not supply the GLP-1 drug but depend on the patient's clinical prescription of this drug. Similarly, all participants will be treated with Ocrelizumab for the indication of MS; however, the study will not provide Ocrelizumab as it will be part of the participant's routine clinical care.

Study Procedures

Inclusion Criteria, Aims 1 and 2:

- 1) Diagnosis of MS (2019 revised McDonald criteria) of any type (PPMS, RRMS, SPMS) by a neurologist,
- 2) Adult age 18-70 years,
- 3) BMI $\geq 24.0 \text{ kg/m}^2$,
- 4) Taken at least one dose of Ocrelizumab prior to study entry,
- 5) EDSS < 7.0 ,
- 6) Able to provide individual informed consent,
- 7) MRI available to confirm the diagnosis of MS.

Exclusion Criteria, Aims 1 and 2:

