Participants will have access to their personal study results at the end of the study after the data are locked and the data are presented, including their clinical scores and their biofluid test results. Future test results, if additional tests are performed on stored blood samples, will be reported back to individual participants only if the test results provide a possibility of clinical relevance to the participant.

There will be no interim results reporting to participants. This is to avoid potential biases in the study as many variables are self-reported.

Data Management and Confidentiality:

The data will be kept in a secure file and analyzed using software that included password protections, encryption, and related security features. Computers will be stored in locked offices. All participants will be given unique study identifiers that they will have throughout the study period. A master file of the participants' personal information and unique identifiers will be kept separately from the study's data collection processes online. Data will be transmitted only using institutional software and secure means such as RedCap that has appropriate institutional security features.

Data will be collected online using RedCap using surveys with forced responses before survey completion to minimize missingness of data. Data will be exported to Microsoft Excel and analyzed using statistical software (e.g. R programming language). Surveys will be scored by the study team using the validated, published metrics (e.g. EDSS, FSS, MS-QOL-54). Variables

of interest will be graphed for distribution (i.e. normalcy) and skew. There will be no data imputation. Missing data will be considered missing completely at random. Interim data analyses will occur every 6 months for reporting to the sponsor. A *p*-value of <0.05 is considered statistically significant.

Aim 1:

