Variables that will be collected or measured, as potentially related to the endpoints of interest, include: subtype of MS (relapsing remitting, primary progressive, secondary progressive), prior DMT use (number of prior DMTs, names), history of relapse of MS in the prior 1 year, highest body weight in the prior year, average body weight in the preceding year, comorbid diagnoses (diabetes mellitus, cardiovascular diagnoses, psychiatric (present/absent, duration)), concomitant medications (particularly those that may affect body weight), smoking status (cigarette), alcohol intake (amount), etc.

Regression variables of interest for the outcome of PIRA will be assessed using exploratory univariate regressions of individual variables of interest. These variables will be determined *a priori* and include sex assigned at birth, age at baseline, BMI at baseline, EDSS at baseline, duration of MS disease (from diagnosis), duration of Ocrelizumab (Ocrevus) treatment.

Secondary endpoints will include (1) a change in 25-foot timed walk, (2) MS-QOL-54 scores, and (3) neurofilament light chain levels.

Sample size justification: The proportion of people with PIRA on GLP-1 agonist drugs and Ocrelizumab is unknown. The proportion of patients with PIRA in relapsing MS ranges up to 24% in published reports.¹⁴ In this study, the detectable difference between a known proportion of patients with PIRA and our study group is $\geq 10\%$, with alpha=0.05 and power=0.8. Since participants will not be randomized to no treatment or intentionally discontinued on GLP-1 agonist treatment during the study, there is no comparison group.

All approved data storage platforms, back-up and recovery procedures, and data access controls will be performed in accordance with the data storage policy at Feinberg School of Medicine: <https://www.feinberg.northwestern.edu/it/policies/file-storage.html>

Provisions to protect the privacy interests of participants:

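### The PIRA test has no named reference proportion; the only rate cited is the top of a range in relapsing MS, while all MS types are enrolled and pooled

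*Protocol*

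**What the plan says.** - **Reference.** The sample size justification in the Protocol cites one PIRA rate: "The proportion of patients with PIRA in relapsing MS ranges up to 24% in published reports". It gives no lower end, centre, follow-up time or treatment background. It then states that "the detectable difference between a known proportion of patients with PIRA and our study group is" at least 10%, "with alpha=0.05 and power=0.8". The known proportion is not named. The same paragraph says that the rate on both drugs is unknown and that "there is no comparison group".
- **Population.** The inclusion criteria for both aims admit MS "of any type (PPMS, RRMS, SPMS) by a neurologist", with no cap or stratification by type. Aim 2 has 40 participants.
- **Analysis.** The Aim 2 analysis text (under Data Management and Confidentiality) analyses the data in aggregate and refers to hypothesis testing of PIRA as the primary outcome. The numerical rule compares the enrolment EDSS with the last EDSS, which may be taken at withdrawal. The rule states no confirmation step and no exclusion of relapse-related worsening.
- **MS subtype.** It is collected, but it is not among the five listed subgroupings or the listed regression variables.
- **Intended inference.** The section on potential benefits foresees that, if GLP-1 agonists protect against PIRA in this study, a new therapy may be studied further.
- **Interim looks.** Interim analyses go to the sponsor about every 6 months.

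**The concern.** In a single-arm trial the reference proportion is the whole comparison, so any error in it passes straight into the conclusion. Here it is unnamed, and the one rate on the page differs from the trial in two visible ways: it is the top of a range, and it comes from relapsing MS only.

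Two further matches are not shown. The Protocol does not say that the cited figure was observed over about 72 weeks, or under a rule comparing only the enrolment and final EDSS.

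If the untreated rate in the people enrolled is below the reference, the trial can report a benefit that the drug did not cause. If it is above, a real benefit can disappear or an apparent harm can emerge. Because subtype is in neither listed set of analysis variables, the results as listed would not reveal that the mix of MS types was responsible.

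**Working it through.** **Inputs from the Protocol.** n = 40 (Aim 2); alpha 0.05; power 0.80; detectable difference at least 10%, read as percentage points; one cited rate, 24%. Sidedness is not stated.

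**Assumptions.** 24% is used as the null because it is the only rate given. All background rates and the 30% share of progressive MS are assumed; the Protocol gives none of them.

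**Step 1. The stated detectable difference.** For a one-sample test of a proportion by the normal approximation,

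n = [z_alpha·√(p0(1−p0)) + z_beta·√(p1(1−p1))]² / (p0−p1)².

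With p0 = 0.24 and p1 = 0.14:
- two-sided: [1.960·√0.1824 + 0.842·√0.1204]² / 0.01 = 127.5, so 128;
- one-sided: [1.645·√0.1824 + 0.842·√0.1204]² / 0.01 = 98.9, so 99.

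With 40 people, power is 0.28 two-sided or 0.42 one-sided (exact test: 0.32 either way). With 24% as the null and a fall to 14%, the 10-point figure reproduces only one-sided with all 100 participants (power 0.804). But 60 of those are in Aim 1, whose own primary endpoints are PDDS and self-reported ambulation.

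**Step 2. Decision rule at n = 40 against 24%.** Exact binomial, at most 0.025 in each tail:
- P(X ≤ 4) = 0.0224 and P(X ≤ 5) = 0.0577, so 4 or fewer events reads as benefit;
- P(X ≥ 16) = 0.0181 and P(X ≥ 15) = 0.0394, so 16 or more reads as harm.

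**Step 3. No drug effect, overall background below 24%.** The chance of a false benefit is P(X ≤ 4 | n = 40, p).

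| True overall rate (assumed) | False benefit |
|---|---|
| 10% | 0.63 |
| 12% | 0.47 |
| 15% | 0.26 |
| 20% | 0.08 |
| 24% | 0.022 |

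**Step 4. Both mismatches together, no drug effect.** Overall rate = 0.7 × relapsing rate + 0.3 × progressive rate.

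| Relapsing | Progressive | Overall | False benefit |
|---|---|---|---|
| 10% | 40% | 19.0% | 0.10 |
| 10% | 50% | 22.0% | 0.04 |
| 15% | 40% | 22.5% | 0.04 |
| 15% | 50% | 25.5% | 0.01 |

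The two mismatches pull in opposite directions and largely offset each other here.

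**Step 5. Relapsing rate really is 24%, with 30% progressive.**
- Progressive at 40%: 0.7 × 0.24 + 0.3 × 0.40 = 28.8%. With no effect, false harm is 0.09. A real 10-point benefit (to 18.8%) is found with probability 0.11.
- Progressive at 50%: 0.7 × 0.24 + 0.3 × 0.50 = 31.8%. With no effect, false harm is 0.17. A real 10-point benefit (to 21.8%) is found with probability 0.04.

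If the background were 24%, the same 10-point benefit would be found with probability 0.32.

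**The case against.** **The Protocol never names 24% as the null.** This stands. A reader might infer that the sponsor chose the top of the range as the reference and so tilted the trial towards a finding of benefit. The text does not say so. The supportable fault is that a detectable difference and a hypothesis test are stated without the reference on which both depend.

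**The large false-benefit figures rest on assumed rates.** This also stands. They treat the whole trial as having a rate of 10–15%. Once progressive participants with a higher assumed rate are included, false benefit falls to 1–10%. The documents do not support a claim that the bias runs in a particular direction.

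**The match on duration and definition cannot be judged.** Partly right. The Protocol points to a systematic review that is not at hand, so a mismatch is not proved. It is only that no match is shown.

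**The analysis plan may settle it, and the aims are modest.** The Protocol is open about having no comparison group, and a positive result would only prompt further study. But it fixes alpha, power, a detectable difference, eligibility and pooling itself, and it plans a test. Followed as written, with the only figure it supplies, the comparison is not like for like. That goes beyond missing detail.

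**Conclusion.** The point holds in this form: the reference proportion is unnamed; the only cited rate is an upper end in relapsing MS; and all MS types are tested together with no control arm. The comparison could show a benefit with no drug effect or hide a real one.

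The size depends on rates that the Protocol does not give. Over the assumptions above, false benefit ranges from 1% to 63%, and the chance of finding a real 10-point benefit falls from 32% to 4–11% where the background exceeds 24%. These are illustrations of sensitivity, not predictions. The documents do not determine the net direction.

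**What to change.** Before any interim data are seen:

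1. Name one reference proportion and justify it for the enrolled mix of MS types, the PIRA definition in use and the 72-week window.
2. Add MS subtype to the listed subgroups, and report PIRA for relapsing and progressive participants separately with exact 95% confidence intervals.
3. Show how the conclusion changes over the published range of rates, giving its lower end as well as its maximum.
4. If no matched reference can be justified, report PIRA as an estimate with its confidence interval and make no claim of benefit from a test.

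**Cost.** This is a change of wording; subtype is already collected. The by-type estimates will be imprecise and the claim weaker. A reference weighted by type needs type-specific rates that the Protocol does not supply. Restricting the formal test to relapsing participants leaves fewer than 40 people: with 28 (70% of 40, assumed), 2 or fewer events would be needed, and exact power for 24% to 14% falls from 0.32 to 0.23. The stated 10% detectable difference does not hold against 24% even at 40, so it should be restated at the same time.

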Participants will be enrolled for an estimated 72 weeks: Measurements will be requested every four weeks (i.e. q28 days) on a specifically designed survey instrument for MS participants. Participants will be asked to report medication dosing, adherence to medicine, tolerability, weight, height, and exercise activities. Self-reported scales will be administered to the participants as well (measuring disability, fatigue, mood, and quality of life).

Participants must be currently on Ocrelizumab (last dose within the past <6 months) and currently taking a GLP-1 medication.

Participants will be contacted and interviewed via Zoom every 6 months to ensure study procedures are going as planned, verify data reported on medication and MS disease history, and ensure study procedures are operating smoothly. Participants who do not complete the surveys within 7 days of the scheduled timing will be contacted by a study coordinator by phone up to 3 times. Participants will also be asked to report any medication changes, dose changes, or discontinuations if they occur at any point between study visits.

Participants will be enrolled until a total of 40 individual participants are reached. Study procedures for each group are listed in Tables 1 and 2. All scheduled events will be part of the study and not part of routine clinical care.

Table 1: Measurements of MS Participants in Aim 1 (Cohort): Frequency and Scale

Measure	Frequency of Reporting	Scale
Weight	Monthly	kg or lbs
Height	Baseline	cm or inches
Waist, Hip, Limb Circumferences	Monthly	cm or inches
Ambulation score	Monthly	Kurtzke Scale
Disability Score	Monthly	PDSS
Step Count	Monthly	Average daily number on phone or step counter if available
Fatigue	Monthly	Fatigue Severity Scale
Mood	Monthly	Beck Depression Inventory
Quality of Life	q3 months	MS-QOL-54 survey
Intolerabilities	Monthly	Self-reported, qualitative, categorized – gastrointestinal, injection site, infections, etc.
Adherence	Monthly	Number of doses taken/ Total Prescribed doses of GLP-1
Axonal degeneration	Baseline and end of study (if possible)	Neurofilament light chain (serum)
New attacks or lesions	Ad hoc	Reported event if occurs

Table 2: Measurements of MS Participants in Aim 2 (Single-Arm Open-Label Trial)

	Screening	Baseline	Week 24	Week 48	Week 72	Unscheduled Visit (e.g. Relapse, Early Withdrawal)
Clinical & MS Relapse History	X	X	X	X	X	X

Medication Review	X	X	X	X	X	X
Physical Examination	X		X	X	X	X

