Variables of interest will be reported using descriptive frequency-based statistics (e.g. mean, median, range). Subgroups of interest (e.g. by gender, disability level below or above the median, etc.) will be compared using t-tests and tests of two proportions as appropriate. Repeated measures (e.g. weight) will be graphed and displayed. Change in values will be reported (final minus starting weight). If needed to report an outcome, repeated measures analyses, will be made using generalized linear models. Incidence of tolerability issues will be reported as the number of events per number of person-months of observation available.

Aim 2:

This will be an intention to treat analysis. All participants who enroll in the single-arm study will be analyzed to the end of their study participation, either the end of the planned study period or time of withdrawal. Data will be analyzed in aggregate with descriptive subgroup analyses performed with the following variables and subgroupings of interest: (1) sex at birth, (2) age at enrollment below or above the median age, (3) duration of GLP-1 (72 weeks versus early discontinuation), (4) BMI group (<30.0 kg/m², 30-39.9 kg/m², >40.0 kg/m², and (5) EDSS score at enrollment above or below the median.

The primary outcome measure is PIRA, dichotomized as present or not, as measured by the rater-determined composite functional outcomes score. This includes the EDSS score with contributions by the 9-hole peg test, SDMT, and 25-foot walking test, and will be constructed as presented in the ORATORIO trial for Ocrelizumab in primary progressive MS vs. placebo.

EDSS will be measured pre-GLP-1 (enrollment) and at the participant's end of study (i.e. one of (a) the end of planned study enrollment period, (b) administrative withdrawal, or (c) participant withdrawal). A positive change in EDSS score of 1.0 points with a baseline EDSS of <5.0 or a positive change in EDSS score of 0.5 points or more with a baseline EDSS score of 5.0 or higher will be considered PIRA. EDSS will be captured at each study visit but the first and last EDSS scores will contribute to the assessment of PIRA for the primary study outcome's hypothesis testing. The use of the EDSS scores at each q24week study visit will also be used in a generalized linear model to determine disability level worsening at any timepoint.

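### Forty Aim 2 participants give about 26-33% power, not 80%, for a 10-point difference from the only PIRA rate the protocol cites (24%)

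*Protocol*

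**What the plan says.** The paragraph headed Sample size justification, in the Aim 2 analysis text, states that "the detectable difference between a known proportion of patients with PIRA and our study group is" at least 10%, "with alpha=0.05 and power=0.8". The known proportion is not given. The one rate cited is in the same paragraph: "The proportion of patients with PIRA in relapsing MS ranges up to 24% in published reports". The paragraph adds that there is no comparison group, so the comparison is of one sample with a fixed value.

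The N has to be taken from Study Aims and Participant Population(s), which give 40 for the single-arm Aim 2 and 60 for the Aim 1 cohort.

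The Aim 2 analysis text defines the primary outcome as PIRA "as measured by the rater-determined composite functional outcomes score", and says "the first and last EDSS scores will contribute to the assessment of PIRA for the primary study" outcome's hypothesis test. For Aim 1, Study Endpoints says instead that "patient-derived disability status (PDDS) score, and ambulation score (self-reported) will be the primary endpoints of interest".

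**The concern.** The sentence is the only quantitative justification of the trial's size, and it describes the primary hypothesis test. A reader will take it that a true 10-point difference in PIRA would be missed in 20% of such trials. Forty people are few for estimating a proportion near one quarter: the standard error at 24% is sqrt(0.24 x 0.76 / 40) = 6.8 points, so 10 points is only about 1.5 standard errors. If power is much lower than claimed, a non-significant result could be misread as evidence that GLP-1 agonists do not affect progression. Under Potential Benefits, the protocol ties further study of the class to what this trial shows on PIRA.

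**Working it through.** **Inputs.** n = 40 (Study Aims; Participant Population(s)). Alpha 0.05 and power 0.80 (Sample size justification). Reference p0 = 0.24, the only rate cited; using it as the null value is an assumption. Difference of 10 points, read as absolute, with no direction stated: p1 = 0.14 or 0.34. Two-sided testing is assumed first, then one-sided. No dropout rate is given, so all 40 are taken as evaluable, which favours the claim.

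**Score test.** Power = Phi[(|p0-p1| sqrt(n) - z sqrt(p0(1-p0))) / sqrt(p1(1-p1))], with z = 1.960 two-sided.
- Fall to 14%: (0.6325 - 1.960 x 0.4271) / 0.3470 = -0.590, power 27.8%.
- Rise to 34%: (0.6325 - 1.960 x 0.4271) / 0.4737 = -0.432, power 33.3%.

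**Exact binomial, at most 2.5% per tail.** Under 24%, P(X<=4) = 2.24% but P(X<=5) = 5.77%; P(X>=16) = 1.81% but P(X>=15) = 3.94%. The test therefore rejects at 4 or fewer or 16 or more events. Power is 32.4% at 14% and 26.0% at 34%.

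**Wald formula.** Power = Phi[|p0-p1| sqrt(n) / sqrt(p1(1-p1)) - z]. For a fall: 0.6325 / 0.3470 - 1.960 = -0.137, power 44.5%; one-sided (z = 1.645), +0.178, power 57.1%.

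Power at n=40 from 24%:

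| Method | Two-sided, fall | Two-sided, rise | One-sided, fall | One-sided, rise |
|---|---|---|---|---|
| Score | 27.8% | 33.3% | 42.0% | 44.1% |
| Exact | 32.4% | 26.0% | 32.4% | 37.6% |
| Arcsine | 36.9% | 28.7% | 49.2% | 40.3% |
| Wald | 44.5% | 26.6% | 57.1% | 37.8% |

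**N needed for 80%.** Score: n = [(z_a sqrt(p0(1-p0)) + z_b sqrt(p1(1-p1))) / |p0-p1|]^2. For a fall this is 127.5 two-sided and 98.9 one-sided, so 128 and 99. For a rise it is 152.7 and 121.3, so 153 and 122. Wald: n = (z_a + z_b)^2 p1(1-p1) / (p0-p1)^2. For a fall this is 94.5 and 74.4, so 95 and 75.

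**Where 80% might come from.** With N = 100 and a one-sided score test for a fall: (1.000 - 1.645 x 0.4271) / 0.3470 = 0.857, power 80.4%. At the same N, the Wald formula for a fall gives 82.2% two-sided and 89.2% one-sided. The two-sided score test gives 68.1% for a fall and 63.5% for a rise. Across the four methods, a rise has 54-74%.

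**Difference detectable with 80% power at n=40, two-sided exact.** The references below 24% are assumed values inside the cited range.

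| Reference | Fall (points) | Rise (points) |
|---|---|---|
| 24% | 16.2 | 21.4 |
| 20% | 16.1 | 20.3 |
| 15% | 12.9 | 20.1 |
| 10% | 9.4 (to about 0.6%) | 17.2 |

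Power for exactly 10 points under the same test (fall / rise) is 22% / 30% from 20%, 40% / 28% from 15%, and 45% / 38% from 12%.

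**The case against.** The strongest reply is that 24% is an upper bound which the protocol never equates with its known proportion, so the claim is under-specified and becomes false only once a reference is supplied. Part of this stands. At n=40 some lower references do reach 80%: two-sided Wald from 15% to 5% gives 83%, one-sided exact from 12% to 2% gives 81%, and two-sided exact from 10.5% to 0.5% gives 82%. These rest either on a near-zero PIRA rate or on the Wald formula, and the protocol names no such reference, direction or test.

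A second reply is that the study total is 100 and PIRA is introduced as the study's primary outcome before the text divides by aim. At 100 the 80% is reached for a fall under some formulas, and this may be how the figure arose. It does not rescue the claim. The sentence belongs to Aim 2, whose outcome is rater-scored, while Aim 1 relies on self-report, may be fully remote, and has no rater EDSS in Table 1. Aim 1 is also described as people already on a GLP-1 agonist, who would generally lack the baseline before GLP-1 start that Aim 2 needs.

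It is also fair that the Aim 2 N is missing only from this paragraph, and that test and sidedness are often left to the SAP. Later detail could not make 80% true at 40 participants against 24%.

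**Conclusion.** The concern holds. Against the one PIRA rate in the protocol, 40 participants give 26-33% power for a 10-point difference (two-sided score or exact test) and at most 57% under any method tried, not 80%. A true 10-point difference would be missed about 67-74% of the time rather than 20%. This rests on an absolute difference, a 24% reference, two-sided testing for the main range, and no dropout; any dropout lowers power further. The cited rate is also for relapsing MS, whereas the inclusion criteria admit primary and secondary progressive disease, so its fit as a reference is itself uncertain. Because the figure describes the primary test, it needs to be corrected.

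**What to change.** Replace the detectable-difference sentence with one that states N, reference, test and sidedness. For example: with 40 Aim 2 participants, and 24% as an illustrative reference, a two-sided 5% exact binomial test has 80% power for a fall of about 16 points or a rise of about 21 points; power for a 10-point difference is about 32% for a fall and 26% for a rise.

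Say that 24% is the top of a relapsing-MS range, and give the detectable differences for lower references: falls of about 16, 13 and 9 points and rises of about 20, 20 and 17 points for 20%, 15% and 10%. Plan to report the observed PIRA proportion with an exact 95% confidence interval; 10 of 40, for instance, is 25% with an interval of 12.7% to 41.2%.

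The cost is protocol wording and a less favourable stated detectable difference. No patients are added and the design is unchanged.
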